#### 2.9 Pharmacokinetic endpoints

Pharmacokinetic analysis will be conducted and reported separately other than in the CSR.

CSJ117 plasma concentration data will be listed by treatment, subject, and visit/sampling time point. Descriptive summary statistics will be provided by treatment and visit/sampling time point, including the frequency (n, %) of concentrations below the lower limit of quantification (LLOQ) and reported as zero. Summary statistics will include mean (arithmetic and geometric), standard deviation, coefficient of variation (arithmetic and geometric), median, minimum, and

maximum. Concentrations below LLOQ will be treated as zero in summary statistics and for PK parameter calculations. If at a single time point a substantial number of concentrations are below LLOQ, they may be substituted with a pre-defined value, such as ½ LLOQ for calculation of PK parameters.

Summary serum concentrations would be plotted by visit. Dose proportionality of serum concentrations will be assessed. .

#### 2.11 Patient-reported outcomes

Patient-reported outcomes in this study include ACQ-5, and AQLQ+12, which are discussed respectively in Section 2.7.1.2, Section 2.7.1.3, and Section 2.7.1.4.

#### 2.13 Interim analysis

#### 2.13.1 Safety

IAs are planned for the monitoring of safety data and do not inflate the type I error for the primary efficacy hypothesis testing. Thus no adjustment for multiplicity is required. These analyses will be performed by an external Independent Statistician and an Independent Programmer for an independent external safety DMC. Persons directly involved in the conduct of the clinical trial will not be involved in performing the IA or reviewing the results. The DMC will be provided with reports which are semi-blinded. If necessary, the study treatment can be unblinded by the chair of the DMC. The DMC will review safety data and make recommendations regarding the conduct of the trial and/or alteration of the current protocol, including termination of a treatment arm.

The DMC meetings will occur approximately twice a year.

More details will be outlined in the DMC charter and a separate DMC SAP.

#### 2.13.2 Efficacy

One or more interim analyses may be conducted to support decision-making in relation to the current clinical study, or the future of the sponsor's clinical development plan or in case of any safety concerns from this study or ongoing clinical studies.

### 3 Sample size calculation

For the primary endpoint pre-dose FEV1, we assume a variance of 0.1461 L at week 8, 0.1456 L at week 12, and a covariance of 0.1163 between the week 8 and 12 assessments (based on a recent asthma dose ranging study (Bateman et al 2017) and literature data (Corren et al 2017). On this basis, the average of the week 8 and 12 assessments has a standard deviation of 0.3622 L.

We assume 2:1:1:1:2:2 randomization to placebo, CSJ117 0.5 mg o.d., CSJ117 1 mg o.d., CSJ117 2 mg o.d., CSJ117 4 mg o.d. and CSJ117 8 mg o.d..

With these assumptions 531 patients result in above 80% power (on average across dose response shapes) to have a significant contrast test at the one-sided 2.5% significance level for a maximum treatment effect over placebo of 0.120 L in the absence of missing data. If we assume that 15% of patients will have missing data and if we conservatively assume that these patients will not contribute any information to the primary analysis, 625 patients are needed for the dose response part of the trial. These calculations were performed using ADDPLAN DF 4.0.9.

The precision of the DR curve estimation were obtained from simulations. Specifically, the average half-length of 95% confidence interval of the estimated DR curve is 57.61 mL, and that of the estimated placebo-adjusted DR curve is 76.93 mL.

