12.8 Sample size calculation

12.8.1 **Primary endpoint(s)**

For the primary endpoint pre-dose FEV1, we assume a variance of 0.1461 L at week 8, 0.1456 L at week 12, and a covariance of 0.1163 between the week 8 and 12 assessments (based on a recent asthma dose ranging study (Bateman et al 2017) and literature data (Corren et al 2017). On this basis, the average of the week 8 and 12 assessments has a standard deviation of 0.3622 L.

We assume 2:1:1:1:2:2 randomization to placebo, CSJ117 0.5 mg o.d., CSJ117 1 mg o.d., CSJ117 2 mg o.d., CSJ117 4 mg o.d. and CSJ117 8 mg o.d..

With these assumptions 531 patients result in above 80% power (on average across dose response shapes) to have a significant contrast test at the one-sided 2.5% significance level for a maximum treatment effect over placebo of 0.120 L in the absence of missing data. If we assume that 15% of patients will have missing data and if we conservatively assume that these patients will not contribute any information to the primary analysis, 625 patients are needed for the dose response part of the trial. These calculations were performed using ADDPLAN DF 4.0.9.

The precision of the DR curve estimation were obtained from simulations. Specifically, the average half-length of 95% confidence interval of the estimated DR curve is 57.61 mL, and that of the estimated placebo-adjusted DR curve is 76.93 mL.

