A Safety Extension Study of CSJ117 is planned (CSJ117A12201E1). Patients who successfully complete 12 weeks of treatment or 12 weeks of follow-up in this study (Study CCSJ117A12201C) may be offered participation in the Safety Extension Study; patient participation in the Safety Extension Study will be optional. Patients not entering the safety extension study directly after the treatment period will complete the 12 week follow-up period.

Originally, approximately 625 patients were to be randomized into this study. Subsequent deprioritzation of the program has led to early termination of this study, resulting in actual enrollment of 335 patients. Detailed information regarding sample size calculation is provided in Section 3.

The primary endpoint will be assessed at the end of the treatment period.

Interim analyses (IA) on safety data are planned for an independent external safety data monitoring committee (DMC) to evaluate the safety data. DMC meetings will occur approximately twice a year. Detailed information regarding DMC analysis will be provided in the DMC charter and a separate DMC SAP.

One or more interim analyses may be conducted to support decision-making in relation to the current clinical study, or the future of the sponsor's clinical development plan or in case of any safety concerns from this study or ongoing clinical studies.

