#### Step 1 (Testing an overall dose-response signal - MCP part):

The covariate adjusted least-squares means averaged across Week 8 and Week 12 visits for each individual dose group and the corresponding variance-covariance matrix will be obtained from a linear mixed effects model for repeated measures (MMRM) with terms for baseline FEV1, visit, treatment, randomization strata – eosinophil count (EOS) ( $\geq$  300 or < 300 cells/µl) and region, treatment-by-visit interaction, and baseline FEV1-by-visit interaction, FEV1 prior to inhalation, and FEV1 within 30 min post inhalation of salbutamol/albuterol (components of reversibility test results at the run-in visit) as fixed effects. To allow adjustment for correlations between time points within patients, an unstructured variance-covariance structure will be used.

The adjusted treatment means from the MMRM will be used to test the null hypothesis of a flat DR relationship for the primary efficacy endpoint at a two-sided significance level of 5% against the alternative hypothesis of a non-constant DR curve. Two one-sided tests will be performed to obtain the two-sided test. The testing will be performed with a multiple contrast test described in the MCP-Mod methodology.

A wide range of possible dose response relationship will be considered to take model uncertainty into account

**Step 2** (Estimation of the dose-response curve and target dose – Mod part):

Once the DR signal is tested, the DR curve and the target dose(s) of interest will be estimated by model averaging. A large number of bootstrap samples from the multivariate normal distribution will be drawn with adjusted means from the MMRM and corresponding covariance matrix. For each sample:

- DR models from the candidate families will be fitted to the data and the best model according to the generalized Akaike information criterion will be chosen.
- The predictions for dose response will be obtained from the best model.

The final DR curve estimate is the median of these predictions while confidence intervals will be calculated from the quantiles. The final DR curve estimate with the model-based two-sided

For business use only

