### 4 Change to protocol specified analyses

Due to depriorization of the program, this study will be terminated early and will have abbreviated CSR instead. The following protocol specified analyses will be removed:

- The mean daily scores of ADSD and ANSD will be analyzed using a similar MMRM as specified for the primary analysis but including the appropriate weeks and baseline as a covariate. The estimated treatment difference (CSJ117 placebo) at each week as well as the average between Week 8 and Week 12 will be reported along with the associated 95% confidence interval.
- The mean of change from baseline in the total daily use of SABA over the 12 weeks of treatment will be analyzed using an ANCOVA model with factors for treatment group, randomization strata (eosinophil count ≥ 300 or < 300 cells/µl, region), as well as baseline total daily SABA use, and baseline pre-dose FEV1 as continuous linear covariates. The estimated treatment difference (CSJ117 placebo) will be reported along with the associated 95% confidence interval.
- The mean daily use of SABA will be analyzed using a similar MMRM as specified for the primary analysis but including the appropriate visits and baseline as a covariate. The estimated treatment difference (CSJ117 placebo) at each week will be reported along with the associated 95% confidence interval.
- Between-treatment differences of the change from baseline in mean morning/evening PEF will be performed using the same ANCOVA models as specified for rescue medication data except that baseline rescue medication use will be replaced with

baseline morning/evening PEF as the covariate. LS mean and associated 95% confidence intervals will be presented for treatments and treatment differences.

- The mean morning/evening PEF will be analyzed using a similar MMRM model as specified for the primary analysis with baseline FEV1 value replaced with the appropriate baseline PEF. The estimated treatment difference (CSJ117 placebo) at each week will be reported along with the associated 95% confidence interval.
- Summary statistics will be provided by treatment and visit/time for each vital signs variable.
- Summary statistics and change from baseline will be provided by treatment and visit/time by each lab variable.

•	The impact of ADA on the efficacy/safety endpoints

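### Does SAP Section 3 need new power and precision figures for the 335 patients actually enrolled?

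*SAP*

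**What the plan says.** SAP Section 3 takes over Protocol 12.8.1 almost unchanged. Its central statement is "531 patients result in above 80% power (on average across dose response shapes) to have a significant contrast test". As in the protocol, the number grows to 625 after allowing for 15% missing, and the calculation assumes a 0.120 L maximum effect and one-sided 2.5%. Section 3 then reports two simulated average half-lengths, 57.61 mL for the dose-response curve, and for the curve relative to placebo: "that of the estimated placebo-adjusted DR curve is 76.93 mL". Neither document says which sample size those half-lengths refer to.

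SAP 1.1 reports the change of circumstances. It gives the planned size: "Originally, approximately 625 patients were to be randomized into this study". It then explains why that number was not reached: "Subsequent deprioritzation of the program has led to early termination of this study, resulting in actual enrollment of 335 patients". Its next sentence points the reader to Section 3 for the details of the calculation.

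SAP Section 4 opens with "Due to depriorization of the program, this study will be terminated early and will have abbreviated CSR instead" and then lists analyses that are dropped. Power and precision do not appear there. The primary test is kept (SAP 2.5.2, Step 1): the adjusted means serve to "test the null hypothesis of a flat DR relationship for the primary efficacy endpoint at a two-sided significance level of 5" percent, followed by model-averaged estimation of the curve.

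**The concern.** A reader who meets 335 in SAP 1.1 is sent straight to Section 3 for the sample size, and finds a present-tense account of a trial nearly twice as large (625/335 = 1.87). The only power figure in the SAP is above 80%, and the only precision figures are those of the planned trial. Because the dose-response test is kept, a non-significant result might be set against that figure and read as fair evidence of no effect, when the planning assumptions imply clearly lower power at 335. The half-lengths pose a second difficulty: with no sample size attached, they cannot be rescaled with confidence.

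**Working it through.** **Inputs.** From SAP Section 3: variances 0.1461 and 0.1456, covariance 0.1163, stated SD 0.3622 L, maximum effect 0.120 L, one-sided 2.5%, allocation 2:1:1:1:2:2, 15% missing. From Protocol 12.4.2: nine candidate shapes (Emax with ED50 0.5, 1, 2, 4; sigmoid Emax with the same ED50 and Hill parameter 3; quadratic with parameter -0.1). From SAP 1.1: 335 enrolled. The number evaluable is not in the documents. It is taken as 335 (none missing) or 335 × 0.85 = 284.75, about 285 (the planned 15%).

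**1. The SD.** √[(0.1461 + 0.1456 + 2 × 0.1163)/4] = √0.131075 = 0.3620 L, against 0.3622 stated.

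**2. The inflation.** 531/0.85 = 624.7, so 625. Reproduced.

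**3. The power.** For a shape with arm means μᵢ and arm sizes nᵢ, the optimal contrast has noncentrality √[Σ nᵢ(μᵢ − μ̄)²]/SD, where μ̄ is the weighted mean. Power is the chance that the largest of the nine correlated contrast statistics exceeds its critical value, about 2.31 by simulation. That value depends on the allocation ratio and not on the total sample size.

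One example, Emax with ED50 1 mg, scaled to a maximum of 1 at 8 mg: the values at 0, 0.5, 1, 2, 4 and 8 mg are 0, 0.375, 0.5625, 0.75, 0.9 and 1. The weighted mean is 5.4875/9 = 0.6097, the weighted mean square is 4.6395/9 = 0.5155, and the weighted SD is √(0.5155 − 0.3718) = 0.379. The noncentrality is (0.120/0.3622) × √531 × 0.379 = 2.89 at 531 and 2.30 at 335. Allowing for all nine contrasts, power for this shape is 80% and 60%.

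Over all nine shapes, each scaled to 120 mL at its best tested dose:

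| Evaluable | Average power | Range by shape |
|---|---|---|
| 531 | 81% | 74–89% |
| 335 | 62% | 54–71% |
| 285 | 55% | 47–64% |

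The first row reproduces the SAP. As a second check, Protocol Table 12-1 pairs a pooled SD of at most 315 mL with 466 patients: 466 × 0.85 = 396 evaluable gives 81%, in line with the table's 80% target. The lowest value in each row is the quadratic. Placing its 120 mL peak at 5 mg, which is not a studied dose, lowers that value to about 50% at 335 and moves the average by less than one point.

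**4. The sample size behind the half-lengths.** Simulating the bootstrap model averaging gave 57.1–57.4 and 75.6–76.7 mL at 531, and 53.2–53.7 and 70.9–71.2 mL at 625. Monte Carlo error at these sizes was about 0.3 mL for the curve and 0.8–1.0 mL relative to placebo. The stated 57.61 and 76.93 mL therefore fit 531. This rests on assumptions about fitting bounds and on averaging over doses and shapes.

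**5. The half-lengths at the achieved size.** Scaling by √(531/335) = 1.259 gives 72.5 mL for the curve and 96.9 mL relative to placebo. Direct simulation gives about 71 and 94–97 mL. At 285, √(531/284.75) = 1.366 gives 78.7 and 105.1 mL, and simulation gives about 76 and 103–106 mL.

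**6. What uses these figures.** The MCP step uses the fitted means and their covariance matrix. The bootstrap step draws from the same two quantities. Neither refers to planned power or planned half-length, and the SAP states no decision rule that does.

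**The case for a change.** The case for a change is that the SAP was brought up to date elsewhere. It has an 8-week follow-up for patients affected by termination (1.1), treats termination as a reason for stopping in the supplementary analysis (2.5.4), and lists dropped analyses (Section 4). Leaving Section 3 alone then looks like an oversight, in a section that 1.1 expressly points to. Observed intervals show achieved precision but not the power of the retained test, and a label with one or two sentences would cost almost nothing.

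The description is right, and the drop from 81% to 62% or 55% is not trivial. Three things blunt it. The power statement names the 531 patients it applies to, so it stays true whatever number enrolled and does not contradict 335. SAP 1.1 tells the reader, just before the pointer, that 625 was the planned number. And a null result is properly read from the estimated effects and their intervals, which SAP 2.5.2 presents for the fitted curve and for each dose group.

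The silence of Section 4 is weak support, since that section covers changes to analyses and a sample size justification is not one. The missing sample size for the half-lengths is a genuine omission, but Protocol 12.8.1 has it too, so it did not arise from the early stop.

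**Conclusion.** No change to the plan is needed. Section 3 is a correct record of how the trial was planned, and it makes no claim about the trial as delivered. It lacks a label saying so and a sample size for the half-lengths, which by simulation appears to be 531. Both are reporting omissions that a reader of SAP 1.1 and Section 3 together can largely fill.

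Under the planning assumptions, average power at the achieved size is about 62% with all 335 evaluable and about 55% with 285; the placebo-adjusted half-length is roughly 94–97 or 103–106 mL. These figures assume the planned SD of 0.3622 L, a 120 mL maximum within the tested doses, and an evaluable number the documents do not supply. Partial data used by the mixed model would improve them; extra missing data from termination would worsen them.

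That uncertainty is a further reason not to write a revised power into the SAP. Enrolment ended because the programme lost priority, not to reach a new target, so the figure could guide no decision, and following the SAP as written gives the same test result, estimates and intervals.

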### 4 Change to protocol specified analyses

Due to depriorization of the program, this study will be terminated early and will have abbreviated CSR instead. The following protocol specified analyses will be removed:

- The mean daily scores of ADSD and ANSD will be analyzed using a similar MMRM as specified for the primary analysis but including the appropriate weeks and baseline as a covariate. The estimated treatment difference (CSJ117 placebo) at each week as well as the average between Week 8 and Week 12 will be reported along with the associated 95% confidence interval.
- The mean of change from baseline in the total daily use of SABA over the 12 weeks of treatment will be analyzed using an ANCOVA model with factors for treatment group, randomization strata (eosinophil count ≥ 300 or < 300 cells/µl, region), as well as baseline total daily SABA use, and baseline pre-dose FEV1 as continuous linear covariates. The estimated treatment difference (CSJ117 placebo) will be reported along with the associated 95% confidence interval.
- The mean daily use of SABA will be analyzed using a similar MMRM as specified for the primary analysis but including the appropriate visits and baseline as a covariate. The estimated treatment difference (CSJ117 placebo) at each week will be reported along with the associated 95% confidence interval.
- Between-treatment differences of the change from baseline in mean morning/evening PEF will be performed using the same ANCOVA models as specified for rescue medication data except that baseline rescue medication use will be replaced with

baseline morning/evening PEF as the covariate. LS mean and associated 95% confidence intervals will be presented for treatments and treatment differences.

- The mean morning/evening PEF will be analyzed using a similar MMRM model as specified for the primary analysis with baseline FEV1 value replaced with the appropriate baseline PEF. The estimated treatment difference (CSJ117 placebo) at each week will be reported along with the associated 95% confidence interval.
- Summary statistics will be provided by treatment and visit/time for each vital signs variable.
- Summary statistics and change from baseline will be provided by treatment and visit/time by each lab variable.

•	The impact of ADA on the efficacy/safety endpoints

#### 5 Appendix

#### 5.1 Imputation rules

#### 5.1.1 Study drug

Missing/partial start date or end date of double-blind treatment will not be imputed.

#### 5.1.2 AE date imputation

Partial AE start and end dates will be imputed. If there is uncertainty whether an AE occurred on-treatment or not, imputation will be performed, such that AE will be considered as on-treatment. Rules for imputing AE end date or start date will be provided in Programming Dataset Specification (PDS) document in details.

#### 5.1.3 Concomitant medication date imputation

Rules for imputing the CM end date or start date will be provided in Programming Dataset Specification (PDS) document in details.

#### 5.2 AEs coding/grading

The MedDRA version which will be available at the time of database lock, will be used for the coding purpose of the adverse events.

#### 5.3 Laboratory parameters derivations

The following table shows the direction of interest when analyzing worst case values in form of maximum and/or minimum post-baseline values. If the direction of interest is given as "High" the maximum value will be calculated and used as worst value, if the direction is given as "Low" the minimum value will be taken, and if it is given as "Low and high", both the minimum value and the maximum value will be calculated and presented in summary tables.

Table 5-1	Breedons of Inter	est for worst case value for laboratory parameters
Laboratory Parameter		Direction of interest for worst case value
A. Hematology		
Hemoglobin		Low
Hematocrit		Low
Erythrocytes		Low
WBC		Low and high
Basophils		High
Eosinophils		High
Lymphocytes		Low and high
Monocytes		High
Neutrophils		Low and high
Platelets		Low and high
B. Chemistry		
Albumin		Low
Alkaline Phosph	natase	High
ALT/SGPT		High
AST/SGOT		High
Bilirubin Total		High
Blood Urea Nitr	ogen (BUN)	High
Creatinine		High
Gamma GT		High
Potassium		Low and high
Magnesium		Low and high
Calcium		Low and high
LDH		High
Phosphorus		Low and high
Sodium		Low and high
CRP		High
Fibrinogen		High
HbA1c		Low and high

 Table 5-1
 Directions of interest for worst case value for laboratory parameters

The following table shows the criteria for clinically notable laboratory values. Not all parameters have notable criteria defined:

Laboratory parameter (unit)	Lower bound of clinically notable range	Upper bound of clinically notable range
Hematology		
Hematocrit (v/v)		
Male	0.37	
Female	0.32	
Hemoglobin (g/L)		
Male	115	
Female	95	
Platelets (x10E9/L)	75	700
WBC (x109/L)	2.8	16.0
Chemistry		
Albumin (g/L)	25	-
Alkaline Phosphatase (U/L)	-	3xULN
ALT/SGPT (U/L)	-	3xULN
AST/SGOT (U/L)	-	3xULN
Bilirubin Total (mcmol/L)	-	34.2
BUN (mmol/L)	-	9.99
Creatinine (mcmol/L)	-	176.8
Gamma GT (U/L)	-	3 x ULN
Potassium (mmol/L)	3	6
Magnesium (mmol/L)	0.51	1.07
Sodium (mmol/L)	125	160
v = volume, ULN = upper limit c	f normal	-

